14.3 Correlative Endpoints Statistical Considerations

The study is not powered to detect specific hypotheses. Due to the small sample size, the correlative studies will be exploratory and hypothesis generating in nature. These analyses will help better identify patients having the potential to benefit from this therapy and aid in designing larger phase III studies.

- I. To evaluate the baseline characteristics of sarcoma tumors (pre-treatment biopsy sample) evaluated in this study including the level of 1001, kynurenine and PD-1/PD-L1 expression, presence of tumor infiltrating lymphocytes (TILs) and tumor antigens, gene expression profile, and the T-cell receptor clonality in tumor-infiltrating lymphocytes (TIL). Descriptive statistics will be used to report the baseline tumor characteristics with respect the level of 1001, kynurenine and PD-1/PD-L1 expression, presence of tumor infiltrating lymphocytes (TIIs) and tumor antigens, gene expression profile, and the T-cell receptor clonality in tumor-infiltrating lymphocytes (TIL).
- II. To assess the potential effect of epacadostat and pembrolizumab on selected biomarker expression measured in pre- and post-treatment tumor tissue and the association between these biomarkers and with clinical outcome, including characterization of 100-1, PD-1/PD-L1, kynurenine expression, tumor infiltrating lymphocytes (Tlls) and tumor antigens, gene expression profiling, characterization of T-cell receptor clonality in tumor-infiltrating lymphocytes (TIL). The pre- and post-treatment measurements will be compared using the paired t-test for each of these biomarkers. The associations with the selected biomarkers, in terms of both the pre-treatment measurement and the difference between pre- and posttreatment measurements, will be evaluated using the two-sample t-test for clinical outcome such as response and clinical benefit, and using survival data analysis (including Kaplan-Meier curve and Cox Proportional Hazards models) for survival outcomes such as progression-free survival and survival. More specifically, Kaplan-Meier curve and Cox Proportional Hazards models will be used for analyzing pretreatment measurement; Kaplan-Meier curve at a landmark time point and Cox Proportional Hazards models allowing for time varying coefficients will be used for analyzing the difference between pre-and post treatment measurements.
- III. To evaluate associations between selected biomarkers measured in serial peripheral blood over time with clinical efficacy, including immunophenotyping and functional analyses, evaluation of serum levels of chemokines, cytokines and other immune mediators, and characterization of T-cell receptor clonality in peripheral blood.
 - Summary statistics will be used to for describing changes across time. In addition the time course of biomarker measurements will be investigated graphically, by summary plots or individual patient plots; their trends over time will be categorized either by visual inspection (if there are clear trend groups such as monotonically increasing or

monotonically decreasing) or by pattern recognition methods such as K-means clustering. The associations with the observed trend in selected biomarkers analyzed will be evaluated using categorical data analysis (including Fisher's exact test and logistic regression) for clinical outcome such as response and clinical benefit, and using survival data analysis (including Kaplan-Meier curve and Cox Proportional Hazards models) for survival outcomes such as progression-free survival and survival.

IV. To evaluate the association between baseline tumor mutational burden and neoantigen production with clinical efficacy of the study therapy.

The associations with baseline tumor mutational burden and neoantigen production will be evaluated using categorical data analysis (including Fisher's exact test and logistic regression) for clinical outcome such as response and clinical benefit, and using survival data analysis (including Kaplan-Meier curve and Cox Proportional Hazards models) for survival outcomes such as progression-free survival and survival.

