Pembrolizumab	200mg	Every 3 weeks	Day 1 of each 3 week cycle	IV infusion

Figure 1. Study Schema

The hypotheses for this study include:

Primary hypothesis

1. Epacadostat given in combination with pembrolizumab, will ellicit an enhanced immune response in patients with advanced sarcoma with antitumoral effect, as assessed by RECIST 1.1.

Secondary hypotheses

- 1. Epacadostat, given in combination with pembrolizumab will be safe and well tolerated in patients with advanced sarcomas.
- 2. Epacadostat, given in combination with pembrolizumab, will improve progression free survival and overall survival in patients with advanced sarcoma as assessed by RECIST 1.1 and irRECIST.
- 3. Epacadostat, given in combination with pembrolizumab, will ellicit an enhanced immune response in patients with advanced sarcoma with antitumoral effect, as assessed by irRECIST.

Exploratory hypotheses

- 1. Baseline characteristics of the immune micorenvironment of sarcoma tumor tissue will vary depending on the sarcoma histological subtype.
- 2. Epacadostat given in combination with pembrolizumab, will alter immune related characteristics of tumor tissue in ways that may correlate with clinical outcome.
- 3. Epacadostat given in combination with pembrolizumab, will alter immune related characteristics of peripheral blood in ways that may correlate with clinical outcome
- 4. Epacadostat, given in combination with pembrolizumab, will benefit a substantial portion of patients with advanced sarcomas. Baseline tumor mutational burden and neoantigen production and and patient-specific immune characteristics,may correlate with clinical efficacy of the study therapy

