4.0 OVERVIEW OF STUDY DESIGN/INTERVENTION

4.1 Design

This is a single-center, phase II study to evaluate the efficacy of the 1001 inhibitor, epacadostat, given in combination with the anti-PD1 monoclonal antibody, pembrolizumab, for patients with metastatic and/or locally advanced grade sarcomas.

A total of 30 patients will be enrolled onto the study. Patients will be enrolled onto one of 4 cohorts. Each cohort will enrol a prespecified number of patients with certain sarcoma histological subtype(s). The 4 patient cohorts and the number of patients eligible to enrol per cohort in this study are as follows:

- A) Undifferentiated Pleomorphic Sarcoma (UPS), Liposarcoma (dedifferentiated or pleomorphic liposarcoma), or Myxofibrosarcoma (n=10)
- B) Leiomyosarcoma (n=5)
- C) Vascular Sarcoma Subtypes (including angiosarcomaEpithelioid Hemangioendothelioma (EHE))) (n= 5)
- D) Other (n=10)

This study will be conducted using a one-stage design. Patients will receive the recommended phase II dose (100mg bid) of epacadostat, when administered in combination with pembrolizumab. Epacadostat 100mg will be administered orally, twice daily, continuously for 21 days. Pembrolizumab will be administered at a dose of 200mg every 21 days (±3 days). Treatment with epacadostat and pembrolizumab will start on day 1 of the first cycle. Each cycle will consist of 21 days.

Patients will be evaluated radiographically at baseline, week 8 (+/- 7 days) and every 8 weeks(+/- 7 days) subsequently until week 56 and then every 12 weeks thereafter or as per the discretion of the treating investigator. Response will be assessed using RECIST v1.1 (primary response assessment) and immune-related response evaluation criteria of solid tumors (irRECIST) (secondary response assessment).

All study participants where feasible will undergo mandatory tumor biopsies at baseline and week 7. Optional biopsies at progression will be offered. Biopsies must be collected within +/- 7 days of the originally scheduled timepoint. Serial blood samples will be obtained at baseline, during, and at the end of study treatment.

Study therapy should continue once there is no evidence of progression of disease per RECIST 1.1, no clear clinical deterioration and the patient is able to tolerate the treatment. Treatment beyond progression will be allowed at the discretion of the clinical investigator

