14.0 BIOSTATISTICS

14.1 Primary Endpoint

The primary objective is to evaluate the efficacy, as assessed by the best objective response rate (complete response + partial response) by 24 weeks by RECIST 1.1. The study will use a one stage design based on the exact binomial test. A 10% response rate will be considered not promising; a 30% response rate will be considered promising. There will be a maximum accrual of 30 patients to this study. It will be concluded that the true response rate is > 10% if there are 6 or more patients with an objective response among 30 patients. The design has a type I error rate of 0.07 and a type II error rate of 0.08. This design provides 92% probability of a positive result if the true response rate is at least 30%, and a 93% probability of a negative result if the true response rate is 10% or lower.

The patient population in this study represents patients with locally advanced/metastatic sarcoma that have received at least one line of previous therapy. The data supporting the 10% null rate comes from the SARC028 study that evaluated the efficacy of pembrolizumab monotherapy among patients with advanced/metastatic sarcoma which is discussed further below. In assessing the efficacy of a combination therapy incorporating pembrolizumab in this study population a response rate of> 10% would be preferred to determine the therapy as having a signal of efficacy.

Patients evaluable for efficacy analysis will include all patients who have received at least one cycle of treatment with epacadostat and pembrolizumab and are assessable for response. Patients who are missing an assessment of response post baseline will not be considered evaluable for response unless they missed the assessment due to progression of disease or treatment related toxicities in which case they will be considered non-responders for that time point. Patients who miss an assessment of response post baseline for any reason other than progression of disease and treatment related toxicity will be replaced.

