Are knowledge regarding the efficacy of immunotherapy in sarcoma is evolving. As previously outlined, two studies evaluating the role of anti-PD1 monotherapy in patients with sarcoma were presented at the ASCO annual meeting in 2016. One study confirmed that no responses were seen among 12 patients with uterine LMS treated with nivolumab.²¹ The second study evaluated pembrolizumab in bone and soft tissue sarcomas (SARC028).²⁰ Signals of efficacy were observed in patients with UPS, liposarcoma (poorly differentiated/defferentiated) and chondrosarcoma. The objective response rates observed in this study was 19% for soft tissue sarcoma and was 5% for bone sarcoma. The objective response rates observed in this study for specific histologic subtypes were as follows: UPS -44%; liposarcoma -22%; synovial sarcoma 11%; leiomyosarcoma - 0%; chondrosarcoma - 17%; ewing's sarcoma - 0%; osteosarcoma - 5%. In relation to this trial design, patients with sarcoma subtypes where limited benefit from anti-PD1 monotherapy was observed in

previous studies may benefit from the combination immunotherapy approach offered in this study. Therefore, patients will be accrued based on histological sarcoma subtype into one of 4 cohorts. This will ensure that we enroll patients with an adequate spead of sarcoma histologies. Each cohort will enroll a prespecified number of patients with specific sarcoma histological subtypes. Due to the small sample size in each cohort, a sufficiently-powered efficacy analysis for each cohort is not possible however, the objective response rate for i) soft tissue sarcomas ii) bone sarcomas (if applicable depending on enrolment), and iii) within each cohort +/ each histological sarcoma subtype will be examined to look for a potential signal of efficacy.

We expect to accrue approximately 1-2 patients each month and hence expect to finish enrollment in 15-20 months.

The anticipated accrual rate for each cohort is as follows:

- A) Undifferentiated Pleomorphic Sarcoma (UPS)/ Liposarcoma (dedifferentiated or pleomorphic liposarcoma) one patient every month
- B) Leiomyosarcoma one patient every second month
- C) Vascular Sarcoma Subtypes (including angiosarcoma, Epithelioid Hemangioendothelioma (EHE),)- one patient every 3-4 months
- D) Other one patient every second month

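### Baseline tumour-marker and mutational-burden tests in 14.3 II and IV pool the four histology cohorts, so a marker that only tracks histology can look linked to response; report a cohort-stratified result beside each pooled one

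*Combined protocol and SAP*

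**What the plan says.** Section 14.3 II relates the pre-treatment marker level, and its change on treatment, to outcome. For response and clinical benefit, the associations "will be evaluated using the two-sample t-test for clinical outcome such as response and clinical benefit"; for PFS and OS it uses Kaplan-Meier curves and Cox models. Section 14.3 IV says: "The associations with baseline tumor mutational burden and neoantigen production will be evaluated using categorical data analysis", naming Fisher's exact test and logistic regression, with Kaplan-Meier and Cox again for survival. No stratum, covariate or cohort term is named in either item. Section 14.3 I reports baseline markers with descriptive statistics and mentions no breakdown by subtype.

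Other sections treat histology as important:

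- Section 1.0, exploratory hypothesis 1: "Baseline characteristics of the immune micorenvironment of sarcoma tumor tissue will vary depending on the sarcoma histological subtype".
- Section 3.0, on tumour neoantigens, states that sarcoma histologies differ markedly in how much genetic alteration they carry.
- Section 14.1 cites response rates on pembrolizumab alone: "UPS -44%; liposarcoma -22%; synovial sarcoma 11%; leiomyosarcoma - 0" per cent, followed by chondrosarcoma 17%, Ewing's 0% and osteosarcoma 5%.
- Section 4.1 sets cohorts of 10, 5, 5 and 10 patients: A (UPS, liposarcoma, myxofibrosarcoma), B (leiomyosarcoma), C (vascular) and D (other).

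In the statistics section, the cohorts are used to spread enrolment and to describe response rates (14.1). They do not enter any marker analysis.

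**The concern.** If histology influences both the marker and the outcome, a pooled comparison mixes two questions: whether the marker separates responders from non-responders among patients with the same kind of sarcoma, and whether the marker identifies the kind of sarcoma. A marker that is merely high in UPS and liposarcoma could pass as a predictor of response. If a marker runs the other way across cohorts, a real within-histology association can be masked.

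Section 14.3 says these analyses should help identify patients likely to benefit and inform phase III design. A marker that restates the diagnosis adds nothing to selection within a diagnosis, and the pooled test cannot tell the two cases apart.

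**Working it through.** **1. The plan's own figure.** Section 14.3 states no error rate, so the only design figure to reproduce is in 14.1: "A 10% response rate will be considered not promising; a 30% response rate will be considered promising", success "if there are 6 or more patients with an objective response among 30 patients", and "The design has a type I error rate of 0.07 and a type II error rate of 0.08". Exact binomial with n = 30: P(X ≥ 6 | 0.10) = 0.0732; P(X ≥ 6 | 0.30) = 0.9234, so type II error is 0.0766. The stated figures reproduce after rounding. The primary design is not in question here.

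**2. Inputs.** Cohort sizes 10/5/5/10 come from 4.1. The rest are assumptions:

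- Setting 1, response A 33%, B 0%, C 10%, D 8%. A is the midpoint of UPS and liposarcoma, (44 + 22)/2. B is the cited leiomyosarcoma rate. D is the simple mean (11 + 17 + 0 + 5)/4 ≈ 8. C is assumed.
- Setting 2, response 50/10/10/15%, all assumed.
- Marker normal with SD 1, higher in cohort A by a shift d, and unrelated to response within each cohort.
- Two-sided 5% level, because 14.3 gives none.

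**3. Size of the spurious difference.** Expected pooled difference ≈ d × (cohort A share of responders − cohort A share of non-responders).

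- Setting 1: expected responders 3.3 + 0 + 0.5 + 0.8 = 4.6. Shares are 3.3/4.6 = 0.72 and 6.7/25.4 = 0.26, so the difference is about 0.45d. Simulation gave 0.47 SD at d = 1 and 0.71 SD at d = 1.5.
- Setting 2: expected responders 5 + 0.5 + 0.5 + 1.5 = 7.5. Shares are 5/7.5 = 0.67 and 5/22.5 = 0.22, so the difference is about 0.44d.
- Equal response in all cohorts: both shares are 10/30, so the difference is zero.

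**4. Rejection rates when there is no within-cohort association** (simulation, about 2,400 to 2,500 trials per setting; stratified test by permutation within cohort):

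| Response A/B/C/D | d | Pooled t-test | Stratified |
|---|---|---|---|
| 33/0/10/8% | 1 SD | 13.6% | about 5% |
| 33/0/10/8% | 1.5 SD | 20.3% | about 5% |
| 50/10/10/15% | 1 SD | 16.6% | about 5% |
| 50/10/10/15% | 1.5 SD | 27.3% | about 5% |

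A separate simulation of setting 1 (8,000 trials, linear model with cohort indicators) gave 13.2% and 20.3% pooled. It also showed the sensitivity: 7.3% at 0.5 SD and 27.4% at 2 SD. Raising cohort C to 20% lowers the 1 and 1.5 SD figures to 10.6% and 16.5%; putting cohort A at 44% raises them to 18.0% and 31.4%. With 30% response in every cohort, the pooled rate stays at 5.0% to 5.6%. The cohort-adjusted rate was 4.7% to 5.4% throughout.

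**5. Power, in both directions.**

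- True 1.25 SD effect, marker 1 SD lower in cohort A: pooled 31% and 35% (settings 1 and 2); stratified 52% and 64%.
- Same effect, marker not varying by cohort: pooled 62% and 81%; stratified 49% and 65%.
- Response driven only by a marker that is 1.5 SD higher in cohort A (logistic slope 1 per SD): 57% pooled to 36% adjusted at 15% overall response, and 71% to 47% at 25%. A case between these gives about 63% to 42%.

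**6. What cohort does not remove.** With the marker raised only in UPS by 1, 1.5 or 2 SD (assumed subtype mix), the cohort-adjusted test still rejects in 6.8%, 9.2% and 11.7% of trials, against 11%, 18% and 24% pooled.

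The simulations cover the response comparison by t-test. The Fisher, logistic and Cox analyses share the mechanism but were not simulated.

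**The case against.** The strongest counter-argument is that between-histology variation is part of the biomarker hypothesis. Section 3.0 presents the heterogeneity of sarcoma as a reason to study a predictive biomarker in it, and links the lack of ipilimumab responses in synovial sarcoma to that tumour's genetic simplicity. If histology acts on response through mutational load, stratifying removes part of the real signal, and the pooled association is false only against a within-cohort null. This stands, and it is why the stratified test should not decide alone.

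It is also fair that 14.3 declares the work unpowered and hypothesis-generating, attaches no significance level or decision rule, and that logistic and Cox models could carry a cohort term. Silence does not exclude adjustment. But no term is named, the two-sample t-test cannot carry one, and imprecision does not excuse a bias that can be foreseen. Section 16.3 mentions histology-specific determinants of response as an outside site's analysis, without a method, and does not alter 14.3.

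A reader might infer that everything in 14.3 is confounded. The documents do not support that. The paired pre/post t-test compares each patient with himself or herself. Hypothesis 1 concerns baseline tumour tissue only, so change scores (II) and blood trends (III) are affected only if they too differ by histology.

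**Conclusion.** The point holds for the baseline tissue-marker and mutational-burden comparisons with outcome in 14.3 II and IV. As written, they cannot separate a marker informative within histology from one that labels histology. Under the assumed 1 to 1.5 SD shifts in cohort A, the pooled t-test's false-positive rate against a within-cohort null is about 14% to 27%, against about 5% when stratified.

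This needs both the marker and the response to vary by histology. The first is the protocol's own hypothesis. The second is tempting to read as the protocol's expectation for this regimen, but the 0% to 44% rates are for monotherapy, and 14.1 hopes the combination will help the low-response subtypes. If it equalises response, the inflation disappears.

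Two further readings go too far. One is that a pooled-only association is spurious: it may reflect histology acting through the marker. The other is that cohort adjustment controls for histology: cohorts A and D each mix subtypes with different cited response rates, so some confounding remains. The number analysed may also fall below 30, because biopsies are taken where feasible and exome sequencing is opt-in (10.4, 10.4.1).

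**What to change.** In 14.3 II and IV, beside each pooled marker-outcome test, report a version stratified by or adjusted for enrolment cohort: a within-cohort permutation test or van Elteren test for response and clinical benefit, and Cox models stratified by cohort for PFS and OS. Do the same for change scores and blood trends where they are related to outcome. In 14.3 I, tabulate baseline markers by cohort, since hypothesis 1 is about subtype differences and has no stated comparison.

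State the reading in advance: describe a marker as informative beyond histology only if the stratified result supports it, and describe a pooled-only association as possibly reflecting histology.

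The cost is analysis-plan wording and some extra analysis, with no new patients, samples or visits. The downside should be stated: the stratified test loses power when the marker does not vary by histology (62% to 49%, or 81% to 65%) or itself carries the histology difference (for example about 63% to 42%). With few responders and possibly none in cohort B, stratified estimates will be imprecise. The report should also say that subtype mixing in cohorts A and D leaves residual confounding.

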12.2.1 Disease Parameters

Measurable disease - Measurable lesions are defined as those that can be accurately measured in at least one dimension (longest diameter to be recorded for non-nodal lesions and short axis for nodal lesions) as >20mm by chest x-ray, as >10mm with CT scan or MRI, or >10mm with calipers by clinical exam. All tumor measurements must be recorded in millimeters (or decimal fractions of centimeters).

To be considered pathologically enlarged and measurable, a lymph node must be > 15 mm in short axis when assessed by CT scan (CT scan slice thickness recommended to be no greater than 5 mm). At baseline and in follow-up, only the short axis will be measured and followed.

Note: Tumor lesions that are situated in a previously irradiated area are not considered measurable unless there is evidence of progression after radiation therapy.

Non-measurable disease - All other lesions (or sites of disease), including small lesions (longest diameter <10mm or pathological lymph nodes with 10 to <15mm short axis) are considered non-measurable disease. Bone lesions, leptomeningeal disease, ascites, pleural/pericardia! effusions, lymphangitis cutis/pulmonitis, inflammatory breast disease and abdominal masses (not followed by CT or MRI), are considered as non-measurable.

Target lesions - All measurable lesions up to a maximum of 2 lesions per organ and 5 lesions in total, representative of all involved organs, should be identified as target lesions and recorded and measured at baseline. Target lesions should be selected on the basis of their size (lesions with the longest diameter), be representative of all involved organs, but in addition should be those that lend themselves to reproducible repeated measurements. A sum of the diameters (longest for non-nodal lesions, short axis for nodal lesions) for all target lesions will be calculated and reported as the baseline sum diameters. The baseline sum diameters will be used as a reference to further characterize any objective regression in the measurable dimension of the disease.

Non-target lesions - All other lesions (or sites of disease) including any measurable lesions over and above the 5 target lesions should be identified as non-target lesions and should also be recorded at baseline. Measurements of these lesions are not required, but the presence, absence or in rare cases unequivocal progression of each should be noted throughout follow-up.

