12.4.1 Special note on target lesions that become "too small to measure"

While on study, all lesions (nodal and non-nodal) recorded at baseline should have their actual measurements recorded at each subsequent evaluation, even when very small (e.g.

Memorial Sloan Kettering Cancer Center IRB Number: 17-508 A(8)

Approval date: 07-May-2024

2mm). However, sometimes, lesions or lymph nodes which are recorded as target lesions at baseline become so faint on CT scan that the radiologist may not feel comfortable assigning an exact measure and may report them as being "too small to measure". When this occurs, it is important that a value be recorded on the D2M form. If it is the opinion of the radiologist that the lesion has likely disappeared, the measurement should be recorded as O mm. If the lesion is believed to be present and is faintly seen but too small to measure, a default value of 5 mm should be assigned.

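### Section 14.3 relates biomarkers to tumour shrinkage only through yes/no outcomes; adding a rank correlation with the percent change already measured is a cheap improvement

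*Combined protocol and SAP*

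**What the plan says.** Section 14.3 II compares tissue markers (the pre-treatment value and the pre-to-post difference) between outcome groups; the association is to be "evaluated using the two-sample t-test for clinical outcome such as response and clinical benefit". Parts III (blood-marker trends) and IV (mutational burden and neoantigens) use "categorical data analysis (including Fisher's exact test and logistic regression) for clinical outcome such as response and clinical benefit". All three parts also plan Kaplan-Meier and Cox analyses of PFS and OS. Response is defined in section 12. Clinical benefit is not defined in 14.3.

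The continuous measure behind response is already collected. Under section 12.2.1 the sum of target-lesion diameters is calculated at baseline: "The baseline sum diameters will be used as a reference to further characterize any objective regression in the measurable dimension of the disease". Section 12.4.1 requires that lesions recorded at baseline "should have their actual measurements recorded at each subsequent evaluation", and section 12.1 schedules scans every 8 weeks to week 56. Section 12.3.1.1 then defines partial response as a fall of at least 30% in that sum.

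On size, section 14.1 states: "There will be a maximum accrual of 30 patients to this study". Section 14.3 says openly that the correlative work is exploratory and has no power target.

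**The concern.** The 30% threshold is needed for the primary response rate. It is not needed to ask whether a marker tracks the depth of shrinkage. Section 14.1 sets its benchmarks thus: "A 10% response rate will be considered not promising; a 30% response rate will be considered promising". So only about 3 to 9 of 30 patients are expected to respond. The response comparison sets that handful against everyone else, and within it a patient with 28% shrinkage counts the same as one who progressed. With fewer than two responders the t-test cannot be run.

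Section 14.3 says these analyses should help identify patients likely to benefit and inform phase III designs. At stake is therefore a missed graded signal in hypothesis-generating work, not the primary conclusion.

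**Working it through.** **1. The plan's own figures.** The drug is called active "if there are 6 or more patients with an objective response among 30 patients", and "The design has a type I error rate of 0.07 and a type II error rate of 0.08". By exact binomial, P(X≥6 | 30, 0.10) = 0.073 and P(X≤5 | 30, 0.30) = 0.077. Both agree with the stated values, so the primary design is not in question. Section 14.3 gives no power figure to reproduce.

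**2. Number of responders.** 30 × 0.10 = 3 and 30 × 0.30 = 9. At a 10% rate, P(fewer than 2 responders) = 0.9^30 + 30 × 0.1 × 0.9^29 = 0.042 + 0.141 = 0.18. With 20 usable biopsies (section 10.4 requires them only where feasible) it is 0.9^20 + 20 × 0.1 × 0.9^19 = 0.39.

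**3. Analytic check of the loss.** Assumptions: marker and percent change are bivariate normal with correlation ρ, two-sided 5%, n=30, all measured. Cutting the outcome so that a fraction p are responders gives a point-biserial correlation r = ρφ(z)/√(p(1−p)), with power ≈ Φ(atanh(r)√27 − 1.96). For Spearman, r_s = (6/π)arcsin(ρ/2), with power ≈ Φ(atanh(r_s)√(27/1.06) − 1.96). At ρ = 0.5:
- Spearman: r_s = 0.483, power 0.76.
- p = 10%: r = 0.5 × 0.1755/0.3 = 0.292, power 0.35, loss 41 points.
- p = 20%: r = 0.5 × 0.2800/0.4 = 0.350, power 0.48, loss 28 points.
- p = 30%: r = 0.5 × 0.3477/0.458 = 0.379, power 0.55, loss 21 points.
- A 50% split (assumed for clinical benefit): r = 0.5 × 0.3989/0.5 = 0.399, power 0.59, loss 16 points.

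**4. Simulation, complete scans** (20,000 trials per setting, n=30):

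| ρ | Responders | Spearman | Response t-test | Loss (points) |
|---|---|---|---|---|
| 0.4 | 3 | 56% | 22% | 34 |
| 0.4 | 6 | 54% | 31% | 23 |
| 0.4 | 9 | 55% | 36% | 19 |
| 0.5 | 3 | 77% | 32% | 45 |
| 0.5 | 6 | 77% | 48% | 29 |
| 0.5 | 9 | 77% | 56% | 21 |

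**5. Unscanned patients.** If about 10% of non-responders have no scan and take the worst rank, Spearman power at ρ = 0.5 is about 0.65, 0.66 and 0.69 at response rates of 10, 20 and 30%. The t-test has about 0.31-0.35, 0.49 and 0.56, so the gain is about 13-34 points. At ρ = 0.4 the smallest gain is about 11. Dropping such patients instead is costly: with the four worst of 30 omitted, the gain is only about 0-23 points (ρ 0.3-0.5), against 11-44 with worst rank.

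**6. Clinical benefit.** With the cut assumed at 50%, ρ = 0.5 and complete scans, the benefit t-test has power 0.61-0.62 against 0.76-0.79 for Spearman, a gap of about 14-17 points. With unscanned patients at worst rank the gap narrows, to about 5 points at the least.

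**7. Ranking down for new lesions.** Suppose a further 20-30% of scanned non-responders, chosen independently of the marker, are placed below all other scanned patients. At ρ = 0.5, Spearman against the response t-test becomes 0.40-0.43 v 0.31-0.32, 0.50-0.52 v 0.47-0.50 and 0.57-0.61 v 0.56-0.57 at the three response rates. The benefit t-test has 0.47-0.48, 0.53-0.55 and 0.58-0.59. Across the runs made, the gain over the response test is about 0-20 points, and over clinical benefit about nil.

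**8. Association not graded.** If the marker is shifted by 1.0 SD in responders only, with 6 responders, the t-test has 58% power and Spearman 27%.

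**The case against.** The strongest reply is that the plan concedes limited power and calls these analyses hypothesis generating. Its wording gives outcomes as examples, so percent change is not excluded. That is fair: this is not an error. But leaving the outcome scale open across many markers invites choosing it after the data are seen, and prespecifying it takes a sentence or two.

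A reader might infer that markers are tested only against responder status, so that 28% shrinkage is never distinguished from progression. The documents do not support that. Clinical benefit is a second planned outcome; on its usual reading (response or stable disease, an assumption here) it separates those two patients, and PFS does too. It is still a dichotomy.

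Response is also more than a cut of the target-lesion sum. Sections 12.3.1.3 and 12.4 add confirmation, non-target status and new lesions, none of which the bivariate normal model contains. This objection stands, and step 7 shows that it matters.

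Finally, the power figures concern the t-test in part II. Part IV plans Fisher's exact test and logistic regression. Part III uses trend categories found by eye or by clustering, to which a correlation with a continuous marker does not apply.

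**Conclusion.** The point holds as a cheap improvement. Section 14.3 uses only binary outcomes for tumour shrinkage, while a continuous measure of it is already recorded. For a graded association with correlation 0.4-0.5, two-sided 5% and n=30, the response t-test gives up roughly 10-45 points of power when shrinkage is observed or only about 10% of non-responders are unscanned. A clinical-benefit split at 50% gives up about 5-17. With heavy ranking-down for new lesions, the advantage is about 0-20 points over response and about nil over clinical benefit. The correlation, the alpha, the 50% split and the missing-scan and new-lesion rates are all assumptions; the documents supply none of them.

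It would be tempting to conclude that percent change should become the main analysis, or that the upper end of the range is the general loss. Neither follows. Nothing in the documents says the relation is graded, and the response test is clearly better when a marker differs only in responders.

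**What to change.** In 14.3 II and IV, add beside the planned tests, not in place of them, a prespecified Spearman correlation of the continuous marker with best percent change from baseline in the RECIST 1.1 target-lesion sum by 24 weeks. Patients unscanned because of progression, death or toxicity take the worst rank, in line with section 14.1, which counts assessments missed for progression or toxicity as non-response. Scanned patients keep their measured percent change; ranking down for new-lesion or non-target progression is a sensitivity analysis. In III, compare percent change across the trend groups with a rank test.

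The cost is a few sentences and a little programming, with no new data, visits or patients and no change to the primary design. The downsides are one more exploratory analysis per marker and lower power than the response test when a marker differs only in responders. For that reason the response and clinical-benefit tests stay.
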